Primary Objective	Evaluate the efficacy of combined Vbeam PDL and topical RHOFADÉ cream (Arm 1) for improvement in erythematotelangiectatic rosacea at the 6-month follow-up compared to baseline and compared to RHOFADÉ treatment alone at the 6-month follow-up (Arm 2).
Secondary Objectives	
 • Evaluate the efficacy of combined Vbeam PDL and topical RHOFADÉ cream (Arm 1) for improvement in erythematotelangiectatic rosacea at each treatment visit (pre-treatments 2 and 3) compared to baseline. • Evaluate the efficacy of combined Vbeam PDL and topical RHOFADÉ cream (Arm 1) for improvement in erythematotelangiectatic rosacea compared to RHOFADÉ treatment only (Arm 2) at each study visit (pre-treatments 2 and 3 and 6-month follow-up for Arm 1 and at the 2-, 3-, and 6-month follow-up visits for Arm 2). • Both arms: Evaluate improvement in vessel size at each study visit (1, 2, 3 and 6 months post baseline visit). • Both arms: Evaluate subject satisfaction at each study visit (1, 2, 3 and 6 months post baseline visit). • Both arms: Evaluate overall improvement (investigator and subject) at each study visit (1, 2, 3 and 6 months post baseline visit).
Efficacy Endpoints	
 • Clinician erythema assessment (CEA) – Appendix II. • Subject self-assessment (SSA) 5-point scale – Appendix II. • Investigator and subject assessment, using a Global Aesthetic Improvement (GAI) 5-point scale – Appendix IV, Table 4. • Investigator assessment of Improvement in vessel size – Appendix IV, Table 5. • Subject satisfaction 5-point scale – Appendix IV, Table 6.
Safety Endpoints	
Evaluate the safety of the treatment (Arms 1 and 2):
 
 • Arm 1: Immediate treatment response – Appendix IV, Table 3. • Both Arms: Number, severity and type of any adverse event recorded throughout course of the study. • Arm 1: Discomfort level following PDL treatment – Appendix III.

BACKGROUND

Rosacea is a common chronic skin condition categorized into 4 subgroups based on clinical manifestations: erythematotelangiectatic, papulopustular, phymatous, and ocular [1]. Although the clinical features may

vary with rosacea, the most common primary feature of all subtypes is transient or persistent facial erythema [2,3]. Erythematotelangiectatic rosacea is primarily characterized by flushing and persistent central facial erythema [4].

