Early diagnosis and treatment based on subtype are recommended to halt progression of symptom severity [5]. Flushing is better prevented rather than treated, by avoiding specific triggers, decreasing transepidermal water loss by moisturizers, and blocking ultraviolet light [5]. Nonselective β -blockers and α 2-adrenergic agonists decrease erythema and flushing [5], while pulsed dye laser [5, 6] and intense pulsed light are used for telangiectasias [5]. Pulsed dye laser also addresses the diffuse erythema and enlarged pores characteristic of rosacea [6].

Oxymetazoline hydrochloride 1% cream (RHOFADE[™]) is a newly FDA-approved topical medication for adult rosacea patients. A primarily alpha-1a agonist, oxymetazoline hydrochloride (HCl) is thought to diminish erythema through vasoconstriction [7]. RHOFADE was evaluated for the treatment of persistent erythema associated with rosacea in two identical, randomized, double-blind, vehicle-controlled, parallel-group clinical trials [8]. A total of 489 subjects with persistent facial erythema associated with rosacea were treated with RHOFADE once daily for 4 weeks. An additional 440 subjects with persistent facial erythema associated with rosacea were also treated with RHOFADE once daily for up to one year in a long-term (open-label) clinical trial [8]. Disease severity was graded by the clinician using a 5-point clinician erythema assessment (CEA) scale [4] and by the subject on a similar 5-point subject self-assessment (SSA) scale, on which subjects scored either “moderate” or “severe” on both scales. Composite success, defined as the proportion of subjects achieving at least a 2-grade improvement on both CEA and SSA, was 15% in Trial 1 and 12% in Trial 2 on Day 29 of treatment [8].

Nonpurpuragenic pulsed dye laser (PDL) and intense pulsed light treatment have resulted in significant reduction in cutaneous erythema, telangiectasia and patient-reported associated symptoms of erythematotelangiectatic rosacea [9]. The PDL is an ideal energy-based device to treat the cutaneous vasculature of rosacea, since the 595nm wavelength is strongly taken up by the hemoglobin in blood vessels [6, 10]. With Vbeam 595nm PDL, ultra-long pulse durations reduce purpura while treating the telangiectasias associated with rosacea, which is more comfortable for patients [5, 6].

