A one-week post first PDL treatment safety follow-up visit will be conducted (1wk FU post Tx.1) for Arm 1 subjects. In addition, efficacy and safety evaluations will be performed at each study visit (1, 2, 3 and 6 months post-baseline visit), as shown in Figure 1 below..

Erythema severity will be assessed at baseline and at each study visit. Improvement in erythema severity will be assessed at each post baseline visit. Additionally, investigator and subject questionnaires will be completed. Photography will be performed at each study visit under visible light conditions of the front full face, right and left 45-degree profile and right and left 90-degree profile. VISIA photography may also be performed for spectrometry measurements (optional). Safety assessments will be conducted at each study visit.

Study Flowchart

Primary Efficacy Objective:

To evaluate the efficacy of combined Vbeam Prima PDL treatment and topical RHOFADÉ cream for improvement in erythematotelangiectatic rosacea, at the 6-month follow-up compared to baseline and compared to Arm 2 at the 6-month follow-up (RHOFADÉ drug therapy only).

Secondary Efficacy Objectives:

- Evaluate the efficacy of combined PDL and topical RHOFADÉ cream (Arm 1) for improvement in erythematotelangiectatic rosacea at each treatment visit (pre-treatments 2 and 3) compared to baseline.
- Evaluate the efficacy of combined PDL and topical RHOFADÉ cream (Arm 1) for improvement in erythematotelangiectatic rosacea compared to topical RHOFADÉ cream only (Arm 2) at each study visit (pre-treatments 2 and 3 and 6-month follow-up for Arm 1 and at the 2-, 3-, and 6-month follow-up visits for Arm 2).
- Evaluate subject satisfaction at each study visit (1, 2, 3 and 6 months post-baseline).
- Evaluate overall improvement (investigator and subject) at each study visit (1, 2, 3 and 6 months post-baseline).
- Evaluate improvement in vessel size (investigator) at each study visit (1, 2, 3 and 6 months post baseline visit).

Safety Objectives:

- Evaluate the safety of combined PDL treatment and topical RHOFADÉ cream (Arm 1) during the study.
- Evaluate comfort level associated with PDL treatment (Arm 1).

 Candela Corporation Confidential	Pilot Study to Evaluate Combined Vbeam[®] Pulsed Dye Laser Treatment and RHOFADE[™] (oxymetazoline hydrochloride) Topical Cream for Erythematotelangiectatic Rosacea			
	Protocol #	DHF24671	Rev. Date	June 11, 2018

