Comfort assessment will be performed independently by the subject using a numerical scale response (NSR) scale 0=No pain to 10=Worst possible pain (*Appendix III*). Subjects will be asked to fill out a questionnaire after each PDL treatment (Tx.1 – Tx.3).

Primary Efficacy Endpoint:

- Clinician erythema assessment (CEA): 5-point scale (0=Clear to 4=Severe) at 6-month follow-up compared to baseline.
- Subject self-assessment (SSA) 5-point scale similar to CEA at 6-month follow-up compared to baseline.

Secondary Efficacy Endpoints:

- Investigator and subject assessment of overall changes in skin condition (skin texture, vessel size, flushing), using a Global Aesthetic Improvement (GAI) 5-point scale (0=Excellent improvement to 4=No difference) – *Appendix IV, Table 4.*
- Investigator assessment of improvement in vessel size – *Appendix IV, Table 5.*
- Subject satisfaction 5-point scale (0=Very satisfied to 4=Very dissatisfied) – *Appendix IV, Table 6.*

Safety Endpoints:

- The number, severity and type of any adverse event recorded throughout the study and post-treatment (discomfort (pain), immediate and delayed response).
- Occurrence of expected post-treatment immediate response following each treatment based on a predefined scale (*Appendix IV, Table 3*).
- Discomfort (pain) level using a 10-point visual analog scale will also be recorded after each PDL treatment, using a Numerical Scale Response (NSR) – *Appendix III.*

Study Duration

The duration of the entire study from first subject enrollment to last subject completing the 6-month follow-up, is expected to be approximately 1 year.

Subject Population

Up to 60 healthy male and female adults (greater than 18 years of age), who meet the inclusion and exclusion criteria.

Subjects enrolled in the study can discontinue their participation at any time, for any reason, without prejudice or reduction in the quality of their medical care. In addition, the investigator or the sponsor can terminate a subject's participation in this study to protect the subject's health or if the subject is not compliant with the study protocol and schedule. Subjects may be replaced if withdrawn or lost from the study.

All subjects enrolled into this study must meet the following criteria:

Inclusion Criteria:

1. Subject is a healthy male or female of 18 to 75 years of age.

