2. Subject has erythematotelangiectatic rosacea with clinician erythema assessment (CEA) and subject self-assessment (SSA) of “moderate” or “severe” (Grade 3 or 4).
3. Fitzpatrick Skin Type I – VI.
4. Subject must be able to read, understand and sign the Informed Consent Form.
5. Subject must be willing and able to adhere to the treatment and follow-up schedule and post-treatment care instructions.
6. Subject must be willing to have limited sun exposure for the duration of the study, including the follow-up period up to 6 months post-baseline.
7. Subject is willing to have photographs taken of the treated area that will be used, de-identified, in evaluations and may be used, de-identified, in presentations and/or publications.
8. For female candidates – subject must be post-menopausal, or surgically sterilized, or using a medically acceptable form of birth control during the entire course of the study.

Exclusion Criteria:

1. Subject is pregnant or planning to become pregnant during the study duration.
2. Subject has an active electrical implant anywhere in the body, such as a pacemaker or an internal defibrillator.
3. Subject has an implant in the treated area (such as metal plates or screws) or an injected chemical substance.
4. Subject has a known collagen (connective tissue) disorder, vascular disease, scleroderma or other autoimmune disease (i.e. rheumatoid arthritis, lupus).
5. Subject has a history of diseases stimulated by heat or sun exposure, such as recurrent Herpes Simplex in the treated area, unless treatment is conducted following a prophylactic regimen.
6. Subject has a history of immunosuppression/immune deficiency disorders (including HIV infection or AIDS) or currently using immunosuppressive medications.
7. Having or undergoing any form of treatment for active cancer or having a history of skin cancer or any other cancer in the areas to be treated, including presence of malignant or pre-malignant pigmented lesions.
8. Subject is suffering from significant concurrent illness, such as cardiac disorders, diabetes (type I or II), or pertinent neurological disorders.

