Inclusion/ Exclusion Criteria	X				
Subject # Assignment	X				
Randomization to Study Arm	X				
Pregnancy Urine test	X				
Vbeam PDL test spots, (optional) – Arm 1	X	X		X	
Change to Medical History		X	X	X	X
Photographs, prior to any treatments		X	X	X	X
VISIA photographs, prior to any treatments (optional)		X	X	X	X
Clinician erythema assessment (CEA), prior to any treatments	X	X		X	X
Subject self-assessment (SSA), prior to any treatments	X	X		X	X
Vbeam PDL Treatment – Arm 1		X		X	
Tx Pain Assessment – Arm 1		X		X	
Immediate Treatment Response – Arm 1		X		X	

Visit	Screening /Baseline	Tx 1*/ 1-month FU	1-week (± 2 days) Safety Evaluation	Tx 2 - 3 / 2 & 3-Month FU Visits (4± 1 week)	6-Month (± 2 weeks) FU
Photographs, 10 mins post any treatment (optional) – Arm 1		X		X	
Global Aesthetic Improvement (GAI)		X		X	X
Vessel size assessment		X		X	X
Subject Satisfaction Questionnaire		X		X	X
Adverse Events and Serious Adverse Events	X	X	X	X	X
End of participation (Termination)					X

*For Arm 1, the 1st PDL treatment will be scheduled at approximately 4 weeks following the screening visit.

Screening Procedures

- A brief relevant medical history will be obtained to address inclusion/exclusion criteria for the study.
- Clinician erythema assessment (CEA) and subject self-assessment (SSA) will be obtained to address inclusion criteria for the study. Subjects with “moderate” or “severe” (Grade 3 or 4) are eligible for study participation (*Appendix II*).
- Pregnancy will be assessed for female subjects based on their last menstrual period, ability to become pregnant (surgical sterilization, birth control), and whether they have plans to become pregnant during the 6-month study period.
- The subject will undergo a standard skin exam to determine if they meet the study criteria.
- If the subject meets the criteria for the study, he or she will discuss with the study staff the study procedures, risks, benefits, and commitments associated with enrollment into the study. The staff will then review the consent form in detail with the subject, after which the subject will be given ample time to review the form. The subject will sign a consent form after the subject fully understands the possible risks/benefits of the study and wants to participate in study. The person conducting the session and the investigator will subsequently sign the consent form.

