- Once the consent form is signed, the subject will be assigned the next consecutive subject number and will be randomized to a treatment arm.
- Women capable of childbearing will undergo a urine pregnancy test.

- Skin type will be recorded using the Fitzpatrick Scale.
- Test spots may be performed (optional) for subjects in Arm 1 to determine the subject's response to selected treatment parameters. Test spot locations will be selected by the investigator.
- Subjects in Arms 1 & 2 will be provided with RHOFADE topical cream and instructed to apply once daily, according to the drug insert instructions: apply a pea-sized amount once daily in a thin layer to cover the entire face (forehead, nose, each cheek, and chin) avoiding the eyes and lips.
- The RHOFADE topical cream will be applied daily for 4 weeks prior to the first PDL facial treatment.
- Subjects must discontinue topical use for a 3-day washout period prior to each PDL treatment.

Pre-Treatment PDL Care

In order to minimize pain during laser irradiation, subjects will be offered to use topical anesthetic cream (EMLA), which will be applied to the skin surface 30-60 minutes prior to laser irradiation.

PDL Treatment Procedure

- Treatments will be performed every 4 (± 1) weeks. Subjects in Arm 1 must discontinue topical use for a 3-day washout period prior to each PDL treatment.
- Laser treatment procedures will conform to all laser safety instructions and should be conducted per the procedure described.
- The investigator, all personnel in the treatment room and the subject will wear protective eyewear, appropriately rated for the device wavelength(s) being operated.
- Based on the subject's response to the test spot evaluation (optional) or experience from treatment of prior subjects in this study or in practice, the investigator will select the parameters used for treatment, based on the threshold for nonpurpuragenic settings.
- Parameters include choice of: the 12 mm or 15 mm spot size, the laser fluence, the duration of the laser pulse exposures and the cooling procedure. The investigator will treat the face with the parameters chosen and will document the parameters.
- The treatment area will be photographed before each treatment and at each post-treatment follow-up visit. Optional photography can include photos at 10 minutes (approximately) after each treatment.
- All subjects will be treated as follows:
 - The 12 mm or 15 mm spot size will be used.

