The use of the device used in this clinical study has been determined to present a non-significant risk in accordance with 21 CFR 812.3 for the intended use in this study.

Potential benefits to participating individuals

Subjects may benefit by achieving visual improvement of their erythematotelangiectatic rosacea as a result of treatment in this study. Not all subjects may have complete clearance of their erythematotelangiectatic rosacea.

DATA ANALYSIS

Copies of Case Report Forms and photographs will be collected by the sponsor during the monitoring visit when appropriate and will be used for analysis of efficacy and safety.

Efficacy

The efficacy of combined Vbeam Prima PDL and topical RHOFADÉ cream for improvement in erythematotelangiectatic rosacea compared to baseline will be assessed by clinician erythema assessment, subject self-assessment, and Investigator and subject assessment, using a Global Aesthetic Improvement 5-point scale and subject satisfaction 5-point scale.

Safety

Safety of treatments will be evaluated throughout this study. Each treatment area will be evaluated for severity of purpura, edema, erythema, hyperpigmentation, hypopigmentation, blistering and scarring. All clinical response and complications observed either immediately following each treatment or at follow-up visits will be noted on the data forms. These data will be descriptively tabulated by treatment area.

Pain scores will also be assessed for safety.

Interim and Final Data Analysis

Interim analysis can be performed at any time and used to terminate the study should it seem necessary to do so.

 Candela Corporation Confidential	Pilot Study to Evaluate Combined Vbeam[®] Pulsed Dye Laser Treatment and RHOFADÉ™ (oxymetazoline hydrochloride) Topical Cream for Erythematotelangiectatic Rosacea			
	Protocol #	DHF24671	Rev. Date	June 11, 2018

ETHICS AND GOOD CLINICAL PRACTICE

This study will be carried out in compliance with the following:

- Syneron Candela Standard Operating Procedures.
- Declaration of Helsinki, concerning medical research in humans (Recommendations Guiding Physicians in Biomedical Research Involving Human Subjects, Helsinki 1964, amended Tokyo, 1975, Venice 1983, Hong Kong 1989, Seoul 2008 and Brazil 2013).
- US Code of Federal Regulations (Title 21CFR including parts 50, 56 and 812 governing informed consent and IRB regulations)

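### The primary objective includes Arm 1 versus Arm 2 at 6 months, but the only efficacy analysis described compares the combined treatment with baseline, which cannot show what adding the laser regimen contributes

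*Combined protocol and SAP*

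**What the plan says.** All references are to the combined protocol and SAP.

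- **Objectives.** The synopsis states the primary objective as evaluating the combined treatment "for improvement in erythematotelangiectatic rosacea at the 6-month follow-up compared to baseline and compared to" cream alone (Arm 2) at 6 months. Under Primary Efficacy Objective it is again "compared to baseline and compared to Arm 2 at the 6-month follow-up". The secondary objectives repeat the Arm 1 versus Arm 2 comparison at 2, 3 and 6 months.
- **Endpoints.** Under Primary Efficacy Endpoint, CEA is a "5-point scale (0=Clear to 4=Severe) at 6-month follow-up compared to baseline". SSA is worded the same way. Neither mentions the other arm.
- **Analysis.** The Efficacy paragraph of DATA ANALYSIS says that the effect of the combined treatment "cream for improvement in erythematotelangiectatic rosacea compared to baseline will be assessed by clinician erythema assessment, subject self-assessment" and the other scales. Arm 2 is not mentioned. No estimate, model, test or analysis set is given.
- **Design.** The study is labelled both two-arm randomised and baseline-controlled. Both arms receive the cream at screening (Screening Procedures).
- **Entry.** Inclusion criterion 2 reads "Subject has erythematotelangiectatic rosacea with clinician erythema assessment (CEA) and subject self-assessment (SSA) of" moderate or severe, that is, grade 3 or 4. Table 2 has one combined Screening/Baseline visit, so the qualifying scores are also the baseline scores.

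**The concern.** The between-arm question is the reason to randomise, and it is part of the primary objective, yet the analysis text never reaches it. If the Efficacy paragraph is followed as written, the report will give Arm 1's improvement from baseline. That figure would be positive even if the laser added nothing, for two reasons. Arm 1 subjects use an active cream throughout, apart from the washouts. They are also selected for high scores on the two scales that are then used as outcomes. A reader could take the improvement as evidence for the laser, while the randomised comparison that could address it has no planned analysis.

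**Working it through.** The documents give no alpha, SD, effect size, allocation ratio or sample-size calculation, so there is no planned figure to reproduce. The illustrations assume 1:1 allocation of the maximum of 60, that is, 30 per arm.

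**1. Objective against analysis.** Objectives: Arm 1 versus baseline, and Arm 1 versus Arm 2. Endpoints: 6 months versus baseline. Efficacy paragraph: combined treatment versus baseline. The second comparison has no analysis attached anywhere.

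**2. The cream's share.** The Background section reports that composite success, at least a 2-grade "improvement on both CEA and SSA, was 15% in Trial 1 and 12% in Trial 2 on Day 29 of treatment". If those rates held at 6 months (assumed), 30 Arm 1 subjects would include 30 × 0.12 = 3.6 to 30 × 0.15 = 4.5 such successes with no laser benefit. The documents give no vehicle rate, so this is not the pure cream effect, and this plan does not itself analyse the composite.

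**3. Regression to the mean.** All inputs are assumed.

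- Set-up: observed SD 0.8; true-score SD 0.8 × √reliability; error SD 0.8 × √(1 − reliability); scores rounded to 0–4. Keep candidates with both scales at 3 or more, then re-measure with no treatment effect. There were 2,000,000 candidates per setting.
- Middle case (candidate mean 2.5, reliability 0.7): mean CEA change is −0.19, −0.23 and −0.28 for a correlation between the true CEA and SSA scores of 1, 0.5 and 0.
- Range: about −0.05 (mean 3.0, reliability 0.9, correlation 1) to −0.53 (mean 2.0, reliability 0.6, correlation 0). The large values need a candidate pool in which only about 7% to 15% qualify.
- In 2,000 simulated null trials per setting with 30 per arm, the baseline- and site-adjusted Arm 1 minus Arm 2 difference averaged between −0.007 and 0.006. Randomisation removes this component.

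**4. What a baseline test would show if the laser added nothing.** Assume a paired t test, two-sided 5%, n = 30, critical value 2.045. The noncentrality is (mean improvement ÷ SD) × √30.

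- 0.5 grade, SD 1.0: 0.5 × 5.477 = 2.74; probability of significance 75%.
- 0.5 grade, SD 0.8: 0.625 × 5.477 = 3.42; probability 91%.
- 0.3 grade: 36% (SD 1.0) to 51% (SD 0.8). 0.8 grade: 99% to nearly 100%.

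**5. Precision of the between-arm estimate.** The half-width is 1.96 × SD × √(2/n).

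- n = 30 per arm, SD 0.9: 1.96 × 0.9 × 0.258 = 0.46 grade (0.35 to 0.56 for SD 0.7 to 1.1).
- n = 24 per arm (20% lost): 0.51 (0.40 to 0.62).

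**6. Missing 6-month scores.** Table 2 schedules "Clinician erythema assessment (CEA), prior to any treatments", and Screening Procedures adds "Subjects must discontinue topical use for a 3-day washout period prior to each PDL treatment". Arm 1 scores at months 1 to 3 therefore precede that visit's laser treatment and follow a cream interruption. The month-1 score precedes the first full treatment, although optional test spots are allowed at screening. These scores do not stand for 6-month scores. Setting missing scores to baseline has its own bias. In the middle case with correlation 1, an assumed cream effect of 0.5 and no laser effect, 20% missing in Arm 1 and 10% in Arm 2 gives about (0.20 − 0.10) × (0.5 + 0.19) = +0.07 grade. The reverse pattern gives −0.07, falsely favouring the laser.

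**7. Timing of the contrast.** From Table 2, the third laser treatment falls at about week 4 + 4 + 4 = 12 (10 to 14 with ±1 week twice). The 6-month visit falls at week 26 (24 to 28). The interval is about 14 weeks (10 to 18). The synopsis and the Photographs section give 2 months.

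**The case against.** The strongest reply is that the comparison is planned. It appears in the primary objective in two places and again in the secondary objectives, and the design is labelled two-arm randomised as well as baseline-controlled. The endpoint wording is not restricted to Arm 1, so 6 months compared to baseline may simply define a change score for both arms, with the objectives supplying the contrast. That reading is fair for the endpoints. It does not rescue the Efficacy paragraph, which names only the combined treatment and only baseline.

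A reader might infer that the plan omits the between-arm question or has no endpoint for it. The documents do not support that; what is missing is the analysis. Nor should one infer that the baseline comparison is fully specified by contrast, since it too has no named test, model or analysis set.

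It can also be said that this is a pilot with no stated power or success criterion. That stands as a reason not to demand power or a formal decision rule. It is not a reason to leave out the estimate. Finally, the sizes above rest on assumed inputs. They illustrate direction and plausible scale, and do not predict this trial's result.

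**Conclusion.** The point holds. Part of the primary objective has no analysis, and the comparison that is described cannot take its place, because Arm 1's change from baseline contains the cream's effect and regression to the mean. Under assumed inputs, regression alone is about 0.2 to 0.3 grade in a middle case. A 0.5-grade non-laser improvement gives a significant paired test 75% to 91% of the time with 30 subjects. The mismatch between objective and analysis rests on the text alone and does not depend on these figures.

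A reader might go further and infer that the between-arm difference would isolate the laser or test the synergy hypothesis. It would do neither. It compares a laser-plus-cream regimen, with pre-laser cream interruptions, against continuous cream, and there is no laser-only arm. No blinding is described and both scores are subjective, so the difference can still be biased even though regression to the mean cancels on average.

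**What to change.** In DATA ANALYSIS, under Efficacy:

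- Specify the Arm 1 minus Arm 2 difference at 6 months in CEA and in SSA as the analysis of the between-arm part of the primary objective. Adjust each for its own baseline score and for site, and give a 95% CI. Report the two scales side by side as estimates.
- Include all randomised subjects by assigned arm, including those withdrawn and replaced, which the Subject Population section allows.
- Keep Arm 1 versus baseline as descriptive, and state that it is not evidence of what the laser adds.
- Do not use month 1 to 3 scores as if they were 6-month scores. If a sensitivity analysis sets missing scores to baseline, state that it is biased when dropout differs between arms.
- State the limits: a regimen contrast, not an isolated laser effect or a test of synergy, with subjective scores and no described blinding.

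This changes analysis wording only. CEA and SSA are already scheduled at 6 months in both arms, so no visits or subjects are added. The price is an imprecise and probably less favourable-looking result, about ±0.46 grade under the assumptions above.

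Separately, two sets of statements that help define the contrast must be reconciled. The first is the washout before the first laser treatment: the synopsis gives 2 days there but also 3 days before each treatment, and Study Design and Screening Procedures give 3 days. The second is the time from the third laser treatment to the 6-month visit: 2 months in the synopsis and Photographs section, about 14 weeks from Table 2.
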